## **8.2. Planned number of subjects**

Sample size was calculated based on the primary endpoint, the percentage of subjects achieving seroconversion according to the evaluation at Day 21 after immunization (Visit 7), and testing of the statistical hypothesis of non-inferiority of the test vaccine (Grippol® Quadri) versus the reference vaccine (Grippol® Plus).

The following non-inferiority margin was used for comparative evaluation of immunogenic efficacy in the non-inferiority model:

- upper limit of the two-sided 95 % confidence interval of the difference between parameters (R-T) of subjects achieving seroconversion in the study quadrivalent vaccine and reference trivalent vaccine groups shall not exceed 15 %.

### Justification of the "non-inferiority margin":

In placebo-controlled studies of inactivated influenza vaccines, the seroconversion parameter in placebo group for the study antigens amounts to 0–1 %. The placebo does not contain the respective antigens, so it demonstrates no immunogenic activity [1].

Taking into account the expected seroconversion level in reference groups > 60 % and the minimum limit for influenza vaccines > 40 % of subjects achieving seroconversion, established by the guidelines for harmonization of requirements to influenza vaccine of the Committee for Proprietary Medicinal Products (CPMP), the non-inferiority margin 15 % is significantly below the superiority of the comparator over the placebo, which is appropriate.

For testing of non-inferiority null hypothesis for Grippol® Quadri and Grippol® Plus vaccines, taking into account the following parameters:

Strictly confidential. Proprietary Information.  
[name]

- Power: 80 %
- One-sided significance level: 2.5 %
- Non-inferiority margin: 15 %
- Expected share of subjects achieving seroconversion in Grippol® Plus group: 60 %
- Expected actual difference for the parameter in groups: 1 %

1 % of the calculated sample size for non-inferiority hypothesis, primary dichotomized parameter and uniform assignment into groups (1:1) is based on the following formula [5,6]:

$$n = \frac{(z_\alpha + z_\beta)^2}{(\delta - \Delta)^2} [\pi_1(1 - \pi_1) + \pi_2(1 - \pi_2)]$$

where  $n$  — the number of patients in each group being compared;

$\pi_1$  — percentage of subjects achieving seroconversion in the reference vaccine group;

$\pi_2$  — percentage of subjects achieving seroconversion in the test vaccine group;

$\Delta = \pi_1 - \pi_2$  — the expected difference between percentages of subjects achieving seroconversion in the reference vaccine and test vaccine groups;

$Z$  — critical values of standardized normal distribution;

$\delta$  — non-inferiority margin.

according to the calculation as per the given formula using software package PASS 12, there shall be at least 193 volunteers in each therapeutic group (579 volunteers in total).

Thus, the minimum required sample size should be: 193 volunteers in each of the three groups (579 volunteers in total).

Taking into account the dropout during the study (5 %), the required number of volunteers has to be increased to 204 per group (612 in total).

Accounting for the possible dropout of volunteers at the screening stage (about 25 %), it is planned to obtain a permission from the Ministry of Health of the Russian Federation to conduct a clinical study with a total of **up to 765 volunteers**.

Replacement of discontinued volunteers with backups is not provided for.

### **8.3. Significance level**

Level of statistical significance: bilateral 5 %.

### **8.4. Statistical criteria for suspension and discontinuation of study**

Not provided by the protocol.

### **8.5. Selection of study subjects**

Data analysis is performed in the following populations:

**Safety analysis population.** This population will include all volunteers who received a dose of the vaccine. The whole safety analysis will be provided in that population of volunteers.

**Full Analysis Set (FAS).** This analysis set will include all volunteers from the safety analysis set who had at least one measurement of serum antibody titer to antigens made. This analysis set was used for the analysis of efficacy and immunogenicity.

**Per-protocol population.** This population includes all the volunteers from the full analysis set meeting the inclusion / non-inclusion criteria, having received a dose of the vaccine according to the randomization, who provided data before and after vaccination to asses immunogenicity according to the study schedule, who did not receive any of the prohibited drugs, and who completed the study without any significant protocol deviations. This analysis set will be used for the analysis of immunogenicity parameters.

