### 3. STUDY DESIGN

#### 3.1. Primary and additional study parameters that will be evaluated during the study

##### **Primary immunological efficacy endpoint:**

- The share of subjects achieving seroconversion (the number of volunteers with antibody titer [of at least 1:40] increased more than 4-fold versus baseline [assessed by HAIR]) for antigens: influenza virus type A — H1N1, influenza virus type A — H3N2, influenza virus type B — Yamagata and Victoria lineage, based on assessment at Day 21 after immunization (Visit 7).

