***Telephone calls (Visits 8–11):***

Telephone calls are made on Day 43±5 (Visit 8), Day 64±5 (Visit 9), Day 122±5 (Visit 10), Day 180±5 (Visit 11) and included the following procedures:

- Interviewing on ARI symptoms within the period.
- Assessment for exclusion criteria.
- Recording of concomitant therapy.
- Recording adverse events and intercurrent disorders.

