### **3.5. The duration of participation of subjects in the study, a description of the sequence and duration of all study periods**

The duration of participation of subjects in the study is  $183 \pm 5$  days. The study includes Screening (days (-3)– 0), Vaccination and Post-Vaccination Observation and Efficacy / Safety Evaluation (Days 1–180  $\pm$  5).

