#### **Serologic testing (serum antibody titer test):**

Immunological efficacy (antigenic activity) of the vaccine is evaluated by its ability to induce the specific immune response, which can be identified under laboratory conditions by serum antibody titer to each antigen.

Antibody titer is determined using the hemagglutination inhibition reaction (HAIR), the method recommended by the WHO for influenza vaccine efficacy evaluation. The study is conducted at the central laboratory. As an additional method for 150 volunteers (50 volunteers in each group), a microneutralization assay is planned (the data will be used to evaluate seroprotection). The detailed description of the study methods is provided in the laboratory guide.

Blood samples for antibody titer test and calculation of mean geometric antibody titer will be collected for determination of background antibody titer after the immunization (Visit 0, Screening) and evaluation of functional immune reaction three weeks after immunization (Visit 7, Day 22±1).

Study parameters:

- The share of subjects achieving seroconversion (the number of volunteers with antibody titer [of at least 1:40] increased more than 4-fold versus baseline [assessed by HAIR]) for antigens: influenza virus type A — H1N1, influenza virus type A — H3N2, influenza virus type B — Yamagata and Victoria lineages.

Strictly confidential. Proprietary Information.  
[name]

- Coefficient of increase of mean geometric antibody titer (antigens H1N1, H3N2, Yamagata and Victoria lineages) (assessed by HAIR).
- Geometric mean of serum antibody to antigens titer (assessed by HAIR): influenza virus type A — H1N1, influenza virus type A — H3N2, influenza virus type B — Yamagata and Victoria lineages.
- Seroprotection: share of subjects achieving protective antibody titer (1:40 and more, assessed by HAIR and microneutralization test) to antigens H1N1, H3N2, Yamagata and Victoria lineages.

The detailed instruction on blood and serum sampling, labeling of tubes, storage and transportation of samples is presented in a separate laboratory guide provided by the central laboratory.

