#### *Efficacy analysis*

The following immunogenicity parameters will be presented with the respective two-sided 95 % confidence intervals for antigens and therapeutic groups:

Before and after immunization:

- Geometric mean antibody titers (GMAT).
- The share of subjects achieving seroconversion.

After immunization:

- The share of subjects achieving seroconversion.
- Coefficient of increase of mean geometric antibody titer versus baseline before immunization (GMAT ratio before and after immunization).

Efficacy parameters will be evaluated by available data, without restoration of missing data.

Testing of statistical hypotheses will be performed for Group A (Grippol® Quadri vaccine) as compared with:

- pooled data of groups B and C (Grippol® Plus) for antigens H1N1 and H3N2, separately for each antigen;
- data of group B for Yamagata lineage antigen;
- data of group C for Victoria lineage antigen.

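### The per-protocol set for immunogenicity has no cut-off at Visit 7, so valid titers are dropped for later events that cannot affect them

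*Combined protocol and SAP*

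**What the plan says.** Section 8.5 defines the per-protocol set by several conditions that must all hold: eligibility, the vaccine as randomized, titers before and after vaccination on schedule, and being among those "who did not receive any of the prohibited drugs, and who completed the study without any significant protocol deviations". It then states the purpose of the set: "This analysis set will be used for the analysis of immunogenicity parameters". Section 8.1 counts seroconversion, the primary endpoint, among the immunogenicity parameters.

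The Full Analysis Set (FAS) in the same section is wider. It takes "all volunteers from the safety analysis set who had at least one measurement of serum antibody titer to antigens made" and is also used for efficacy and immunogenicity. Section 8.1 adds: "Efficacy parameters will be evaluated by available data, without restoration of missing data".

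On timing, Section 6.2 places the post-vaccination titer at Visit 7 (Day 22±1), and the visit schedule has no later serology. Section 3.2 then has telephone calls at about Days 43, 64, 122 and 180, each with a check of exclusion criteria and concomitant therapy. Section 3.5 runs participation to Day 180±5. Section 5.2.1 bans some drugs only at screening and on the day of immunization, but bans CNS suppressants, cytotoxic drugs, anticoagulants and antiaggregants (including acetylsalicylic acid) for the whole study.

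**The concern.** The prohibited-drug and completion conditions run to the end of the study, but the data they govern are complete at Visit 7. A sedative on Day 90, loss to follow-up on Day 150 or a serious adverse event on Day 100 removes the volunteer's seroconversion result from the per-protocol analysis, although none of these can alter serum already drawn.

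Two things are at stake. The first is precision. The second is selection, because membership then depends on what happens after the endpoint. The documents contain one path that is not obviously unrelated to vaccine response. Influenza leading to hospitalization is a severe case under Section 6.2, hospitalization is a serious-event criterion under Section 7.3.2, and a serious adverse event is a reason for exclusion under Section 3.6. A later illness that the vaccine is meant to prevent could thus decide whose titers are analyzed. How often this would happen, and which group it would favor, cannot be derived from the documents.

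**Working it through.** **Does any text supply a cut-off?** Providing both titers on schedule is a separate condition in Section 8.5, so meeting it does not excuse a later failure on drugs or completion. A significant deviation is not defined there. A narrow reading might spare late deviations irrelevant to titers, but the drug and completion conditions would still run to Day 180. No other section limits them.

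**How much of follow-up is affected?** Days after the last titer: 180 − 22 = 158, and 158/180 = 88% of follow-up.

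**The plan's own sample size.** Inputs from Section 8.2: reference rate 0.60, true difference (reference minus test) 0.01, hence test rate 0.59; margin 0.15; one-sided 2.5%; power 80%.

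n = (1.960 + 0.842)² × (0.60×0.40 + 0.59×0.41) / (0.15 − 0.01)² = 192.98, so 193 per group, as stated. With 5% dropout, 193/0.95 gives 204 per group and 612 in total, also as stated. The allowance is 204 − 193 = 11 volunteers per group (5.4%), without replacement.

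**Effect of losses on the per-protocol analysis.** The loss rates are assumptions. They cover absence from the set for any reason, not only late events. With n per group after loss, rounded down:

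- B lineage (A against B, or A against C): SE = √[(0.24 + 0.2419)/n]
- H1N1 and H3N2 (A against pooled B and C): SE = √[0.24/(2n) + 0.2419/n]
- Power = Φ(0.14/SE − 1.96); half-width of the 95% interval = 1.96 × SE

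| Assumed loss | n per group | Power, each B lineage | Half-width, B lineage (points) | Power, each A strain |
|---|---|---|---|---|
| 0% | 204 | 82.1% | 9.5 | 91.4% |
| 5% | 193 | 80.0% | 9.8 | 89.9% |
| 10% | 183 | 77.9% | 10.1 | 88.3% |
| 15% | 173 | 75.6% | 10.3 | 86.5% |
| 20% | 163 | 73.1% | 10.7 | 84.4% |

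The half-widths compare with a margin of 15 points. They use the plan's unadjusted formula. The planned primary interval comes from logistic regression with baseline titer as covariate, so they approximate that analysis.

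**The case against.** The strongest reply is that little depends on this. The FAS keeps every affected titer. Section 3.1 labels seroconversion the "Primary immunological efficacy endpoint", and Section 8.5 assigns efficacy to the FAS, so the plan leans towards the FAS for the primary test. If the FAS decides, only a supporting analysis is affected. This stands in part: neither Section 8.1 nor Section 8.5 says which set decides, so the per-protocol result cannot be assumed to be merely supportive.

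A second reply is that the table does not measure the defect. Losses for any reason include missed Visit 7 samples, ineligibility and early deviations, which a cut-off would not recover. This is correct. The table bounds total loss, and the part due to events after Visit 7 could be near zero. The volunteers are healthy adults aged 18 to 60, and the drugs banned after vaccination day are few.

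A third is that the 5% allowance already covers late losses. Section 3.6 ties it to early withdrawal over the whole study, and the Synopsis describes it as volunteers whose data cannot be evaluated. Late withdrawals may well be covered. Whether late prohibited-drug use always leads to withdrawal is less clear: the Synopsis and Section 3.6 direct withdrawal, while Section 5.3 only permits it. No separate allowance is made for volunteers who stay in the study but leave the set.

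Finally, Section 8.7 would let the sponsor correct the set later. That would be a departure from the initial plan needing justification in the report, which a sentence now avoids.

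**Conclusion.** The concern holds. As written, the per-protocol rule discards valid baseline and Visit 7 titers because of events that cannot affect them, and no other text prevents this. The defect is confined to the per-protocol immunogenicity analysis. It bears on the primary conclusion only if that set decides non-inferiority or both sets must agree.

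The size is modest and partly unknown. Once more than 11 of 204 per group are missing for any reason, a B-lineage per-protocol comparison falls below 80% power, reaching about 73% at an assumed 20% loss. The A-strain comparisons stay at about 84% or more over the same range. These figures rest on the plan's 60% and 59% rates and on assumed losses. The share due to late events, and the direction of any selection, cannot be stated. The planned sample size is not in error.

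**What to change.** In Section 8.5, count prohibited-drug use and significant deviations against per-protocol membership only when they occur up to the Visit 7 blood sample, and delete the requirement to have completed the study. Eligibility and receipt of the randomized vaccine are facts of Day 0 and stay as conditions whenever a failure is discovered. The requirement for samples on schedule already ends at Visit 7.

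The cost is one sentence. It needs no new data, visits or volunteers, and it leaves the medication and withdrawal rules untouched. It does not settle which set decides non-inferiority, which the plan still needs to state.

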### **8.6. Procedures for recording missing, falsified data and data that cannot be analyzed.**

The employee who maintains the database, after entering all the data checks the database for inconsistencies, erroneously entered and missing data. If questions arise, the investigator will be sent a form "Questions for investigators", the request for which must be answered in writing within 7 business days after receipt. After receiving answers to the questions, the officer responsible for maintaining the study database checks for inconsistencies, erroneously entered data, and missing data. After the final completion of the collection and data entry of all centers, the database is closed, after which statistical processing can begin.

---

Strictly confidential. Proprietary Information.  
[name]

## **8.7. Procedures for communication on any deviations from the initial statistical plan**

If the application of initially defined statistical methods is not possible, the statistical report and the final report on the study will provide a justification for making changes, with references to the calculations made, statistical indicators and a general analysis of the reasons for these changes. The decision to make extraordinary deviations (assumptions, modifying data) is the competence of the study Sponsor, and must be explained and justified, including in the text of the final report on the clinical study.

## **9. DIRECT ACCESS TO SOURCE DATA / DOCUMENTS**

The investigator and the medical institution where the study is conducted are obligated to provide direct access to source documents (original records or certified copies) to study monitors, auditors, representatives of the medical unit of LEC, as well as to representatives of regulatory authorities.

Direct access to source documents is granted to specified persons for the purpose of verifying the data entered in the CRF, assessing the compliance of the study with the protocol and normative documents, as well as protecting the rights of study subjects. To accomplish these goals, these individuals may conduct study-related monitoring, audits, ethical examinations, and inspections.

## **10. QUALITY CONTROL AND ASSURANCE**

The quality control of this study is provided through monitoring, verification of data against the baseline, audits by representatives of the sponsoring company, standardized data entry and processing. All the above procedures are carried out according to sponsor's standard operating procedures that have been composed in accordance with the requirements of ICH GCP.

### **Training of investigators**

During the initial visit, the trial site monitor will conduct a training on the clinical trial protocol, as well as on all procedures and materials required for appropriate conduct of the study with the study team members.

### **Monitoring of the study**

Study monitors must regularly contact the investigator and visit the trial site. Upon request, the investigator and the medical institution that conducts the study should provide them with direct access to all study documents (CRFs and other documents relevant to the study), subject to the requirements of confidentiality of the personal data of volunteers and conducting an audit in accordance with legal regulations.

---

Strictly confidential. Proprietary Information.  
[name]

The duties of the monitor of the trial site include verification of data entered in the CRF against the baseline data, monitoring of the compliance of the study center with the requirements of the study protocol, monitoring of the compliance with the requirements of the good clinical practice, and monitoring of the compliance with the applicable legal requirements.

The investigator and other staff members at the trial site participating in the clinical study must be prepared to allow time to discuss the data with the clinical study monitor. The investigator should assist the monitor and cooperate with him/her in order to resolve any problems identified during the visits to the trial site.

The frequency of monitor's visits to a trial site depends on a set of study subjects; at the beginning and end of the study, more frequent visits of the monitor to the trial site are possible as compared to the middle of the study.

Before initiation of the study, the monitor verifies that the trial site complies with all of the study requirements and discusses the clinical study protocol and the CRF with the investigator and the rest of the trial site staff responsible for the implementation of key study elements.

During the study, the monitor checks the compliance of the study with all the requirements specified above, including checking the informed consents, records and storage conditions of the study drugs, study documentation, baseline data, and reports on AEs.

When data inconsistencies are identified during the validation of study database, the description of these inconsistencies is addressed to the investigator in a form of data correction forms.

Monitors will be provided with separate guidelines for monitoring the study, containing additional instructions on monitoring procedures.

### **Audits:**

The purpose of the audit by the study sponsor is an assessment of the conduct of study and its compliance with the requirements of the protocol, standard operating procedures, standards for good clinical practice, and applicable legal requirements independent of normal monitoring and quality control procedures. An audit can be conducted in all trial sites and organizations participating in the study.

## **11. ETHICAL ASPECTS**

### **11.1. Helsinki Declaration of the World Medical Association**

The investigator is obligated to ensure that the study is conducted in strict accordance with the Helsinki Declaration of the World Medical Association, adopted in 1964, in a 2013 edition.

---

Strictly confidential. Proprietary Information.  
[name]

## **11.2. Approval by the regulatory authorities**

This study will be conducted in compliance with the requirements of the regulatory authorities of the Russian Federation. In addition to the approval of LEC trial sites before initiation of the study, a study permission must be obtained from relevant regulatory authorities, including the Ethics Council. In addition, all amendments to study documents must be submitted to the regulatory authorities for approval, as well as reports on SUADR, annual reports on the safety of study treatment and notification of the completion of the study.

## **11.3. Approval by the LEC of a medical institution**

Before study drugs are sent to the trial site, and the site begins recruiting study subjects, the LEC of the medical institution must receive a documented approval to conduct the said study, as well as approval of the study protocol, amendments to it (if any), volunteer information sheet and the informed consent form for participation in the study, any other documents provided to the volunteers for promotional purposes, as well as information on payments and compensation to volunteers in the study.

Amendments to study documents, which must be approved by the LEC, take effect only upon receipt by the sponsoring company of a copy of the written approval of the LEC amendment.

If an amendment to the study protocol is necessary in order to eliminate the obvious and immediate risk to volunteers, it can be enforced before the approval of the LEC of the medical institution. However, in this case the approval has to be obtained within the shortest possible period of time after introduction of the amendment.

